2. IDE PROTOCOL

2.1 PURPOSE OF STUDY

The Balloon Spacer (also called "BioProtect Balloon Implant[™] System",) is intended to temporarily position the anterior rectal wall away from the prostate during radiotherapy for prostate cancer and in creating this space it is the intent of the Balloon Spacer to reduce the radiation dose delivered to the anterior rectum. The balloon composed of a biodegradable material that maintains that space for the entire course of prostate radiotherapy treatment and is completely absorbed by the patient's body over time.

This IDE study will demonstrate that the BioProtect Balloon Implant System, when used in prostate cancer patients undergoing radiotherapy by means of IMRT, reduces the radiation dose delivered to the anterior rectum.

2.2 PROTOCOL STUDY CONDUCT

2.2.1 STUDY DESCRIPTION

This study will be a prospective, multi-center, randomized, double-arm, single blind, concurrently controlled study to assess the safety and efficacy of the BioProtect Balloon Implant System in prostate cancer subjects undergoing radiotherapy by means of IMRT. Subjects will be randomized in a 2:1 ratio (balloon implantation:control) to receive either IMRT + marking + balloon implantation or IMRT + marking. The balloon will be inserted during the same session as the marking.

2.2.2 STUDY OBJECTIVES AND HYPOTHESIS

2.2.2.1 Овјестиче

The objective of this clinical study is to demonstrate that the balloon, when properly inserted between the prostate and the rectum is safe and effective in reducing the volume of the rectum receiving greater or equal to 70 Gy (V_{Rectum} 70) by means of IMRT in prostate cancer patients undergoing radiotherapy.

2.2.2.2 PRIMARY EFFECTIVENESS ENDPOINT

The primary effectiveness endpoint will be evaluated in subjects with prostate cancer who are undergoing radiotherapy by means of IMRT and who receive the balloon, with individual patient success defined as a reduction of at least 25% of the volume of the rectum receiving greater or equal to 70 Gy (V_{Rectum} 70) when compared to pre-implantation values. The study will be considered a success if the rate is significantly greater than 75%; the hypothesis will be evaluated using a one-sided exact binomial test as detailed in **Section 2.3**.

2.2.2.3 PRIMARY SAFETY ENDPOINT

The primary safety endpoint is the rate of occurrence of Grade 1 or greater rectal adverse events and implantation procedure related adverse events with a duration of at least 2 days through 6 months. This rate will be compared between the balloon group and the control group, and the study will be considered a success if statistical significance is achieved on a one-sided non-inferiority test. Details appear in **Section 2.3**.

2.2.3 STUDY POPULATION

Two hundred twenty-two (222) men who meet enrollment criteria will be enrolled at up to 25 sites in the US and outside the US. No more than 40 subjects will be enrolled at an individual center. Subjects will all be male and at least 18 years of age, and will have prostate cancer that is locally confined or extracapsular with no posterior extension (i.e., not involving the rectum) with a planned treatment regime of radiotherapy by means of IMRT. A blocked randomization, with randomly varying block sizes, will be used, to minimize the likelihood that the site will be able to infer the next randomization assignment in the sequence.

All subjects who provide Informed Consent, are randomized and marked or implanted will be included in the intent-to-treat population. It is possible that a subject randomized to the Balloon Group may not be marked or implanted due to an arising health concern or may be excluded intraoperatively due to the inability to perform proper dissection between the prostate and the rectum. Preliminary data will be captured for subjects excluded intraoperatively, documenting the reason(s) for exclusion, and these subjects will be excluded from the primary (Per-Protocol) analyses. These subjects will be included a sensitivity analysis as failures for the balloon group. Additionally, sites will maintain a log of screening failures, documenting the reason for failure. Subjects who are screening failures will be excluded from analysis.

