2.2.5 STUDY DESIGN

2.2.5.1 OVERALL STUDY DESIGN

This study will be a prospective, multi-center, randomized, double-arm, single blind, concurrently controlled study to assess the safety and efficacy of the BioProtect Balloon Implant System in prostate cancer subjects undergoing radiotherapy by means of IMRT.

Subjects will be randomized in a 2:1 ratio (balloon implantation:control) to receive either IMRT +marking + balloon implantation or IMRT +marking. The balloon will be inserted during the same session of the marking.

Subjects will be blinded to study assignments. It is not practical to blind the surgeon or surgeon's staff since they will participate in the insertion procedure and/or be responsible for

maintaining source documentation. Additionally, the core lab cannot be blinded since the balloon will be visible on the CT images.

All subjects enrolled in the study will be included in an "intent-to-treat" analysis regardless of failure to complete the required follow-up examinations. Subjects will be considered enrolled in the study for the purposes of an intent-to-treat analysis only after they have provided Informed Consent and have been randomized. Preliminary data will be captured for subjects excluded intraoperatively, documenting the reason(s) for exclusion. It is anticipated that very few, if any, subjects will be excluded intraoperatively. Sites will maintain a log of screening failures, documenting the reason for failure. Additionally, subjects who are randomized but not implanted (e.g., due to an adverse event that prevents or significantly delays their radiation treatment) may be removed from the study. Such removals will be documented and reported appropriately. Subjects who are screening failures or who are removed from the study prior to implantation will be excluded from analysis.

This study will utilize a core laboratory for analysis of CT images. Post implantation CT images for the *Balloon Group* will be compared to pre-implantation images to demonstrate the change in distance and potential for rectal protection provided by the balloon.

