2.3.2 ANALYSIS POPULATIONS

The intent-to-treat (ITT) population consists of all subjects randomized for the study. The primary analysis population will be based on a Per-Protocol population consisting of ITT in the Control Group and subjects who were randomized to the balloon Group. The ITT population analysis will be included in a sensitivity analysis.

The primary analyses will be completed using a Per-Protocol (PP) Population consisting of subjects who were randomized to and received the balloon device or were randomized to the *Control Group*. It is anticipated that there may be one or two subjects that get randomized to the balloon device, but are not implanted. These subjects will not be included in the PP population or be required to be followed per the protocol. However, the subjects will be included as failures in a sensitivity analysis in the primary analyses for the study.

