#### Intent-to-Treat (ITT) Population

Intent-to-Treat (ITT) population will include all randomized subjects, regardless of whether they underwent a surgery or not. All subjects in the ITT population will be analyzed as members of the group to which they were assigned irrespective of actual treatment received.

The ITT population will be used for a sensitivity analysis for the study co-primary endpoints.

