#### **10.3** Evaluations and Statistical Analyses

#### **10.3.1 Subject Disposition**

Subject disposition will include the total number of subjects screened and number of screen failures recorded in the database, which will include any patient who consented to participate whether they failed eligibility or withdrew prior to marking.

Subject follow-up will be summarized by treatment arm at baseline, marking/implantation, postimplantation, 6 months and every 6 months thereafter during the study. For each period, expected followup will be calculated as the number of subjects theoretically reaching that period, minus the number of subjects not yet overdue for that visit and minus any deaths occurring since the last visit. Actual followup for each period will be summarized by frequency and the percentage of expected follow-up. The frequency and percentage of subjects missing a visit window and/or discontinuing the study will be included, along with the reasons for discontinuation.

Study enrollment by location (US and outside US) and by each site will be summarized by the number and percentage of subjects.

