#### Figures

Figure 14.2.1, Average Subject Dosimetry Profile Before and After Implantation, ProSpace Per-Protocol

Figure 14.2.2, Tipping Point Analysis of Primary Effectiveness Endpoint, Intent-to-Treat Population

Figure 14.2.3, Kaplan-Meier Estimates of Cumulative Occurrence of Primary Safety Endpoint, Per-Protocol

Figure 14.2.4, Kaplan-Meier Estimates of Cumulative Occurrence of Grade 2 Rectal Events, Per-Protocol

Figure 14.2.5, Tipping Point Analysis of Primary Safety Endpoint, Intent-to-Treat Population (If analysis has any missing data)

Figure 14.2.6, EPIC Urinary Incontinence Domain Means and Standard Errors by Time and Treatment, Per-Protocol Population

Figure 14.2.7, EPIC Urinary Irritative Domain Means and Standard Errors by Time and Treatment, Per-Protocol Population

Figure 14.2.8, EPIC Bowel Domain Means and Standard Errors by Time and Treatment, Per-Protocol Population Figure 14.2.9, EPIC Sexual Domain Means and Standard Errors by Time and Treatment, Per-Protocol Population

The final listing content will be updated as necessary to include all eCRF data.

Listings
Listing 16.2.1.1, Subject Number and Treatment Status, All Subjects
Listing 16.2.1.2, Screen Failures and Reasons(s) for Failure, Randomized Subjects
Listing 16.2.13 End of Study Status, Intent-to-Treat Population
Listing 16.2.2, Protocol Deviations, Intent-to-Treat Population
Listing 16.2.4.1, Demographic Information, Intent-to-Treat Population
Listing 16.2.4.2, Medical History, Intent-to-Treat Population
Listing 16.2.4.3, Concomitant Medications, Intent-to-Treat Population

Client/Project	BioProtect BP-007
Version and Date	V2 05-DEC-2021

Listings
Listing 16.2.4.4, Study Procedure Information, Intent-to-Treat Population
Listing 16.2.4.5, CT Results, Intent-to-Treat Population
Listing 16.2.6.1, Radiation Dosing and Organs at Risk, Per-Protocol Population
Listing 16.2.6.2, Radiation Visit Summary, Per-Protocol Population
Listing 16.2.6.3.1, EPIC Domain Scores, Intent-to-Treat Population
Listing 16.2.6.3.2, Individual EPIC Responses Part I, Intent-to-Treat Population
Listing 16.2.6.3.3, Individual EPIC Responses Part II, Intent-to-Treat Population
Listing 16.2.6.3.4, Individual EPIC Responses Part III, Intent-to-Treat Population
Listing 16.2.6.3.5, Individual EPIC Responses Part IV, Intent-to-Treat Population
Listing 16.2.6.3.6, Individual EPIC Responses Part V, Intent-to-Treat Population

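### The protocol and SAP disagree on who is in the ITT set: some clauses drop randomised men not marked or implanted, although the formal definitions keep them

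*Protocol*

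**What the plan says.** The clauses fall into three groups.

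**ITT is everyone randomised.** Protocol 2.3.2: "The intent-to-treat (ITT) population consists of all subjects randomized for the study". SAP 9: "Intent-to-Treat (ITT) population will include all randomized subjects, regardless of whether they underwent a surgery or not". Protocol 2.2.5.1 also counts a man for ITT "only after they have provided Informed Consent and have been randomized".

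**Some randomised men are out.** Protocol 2.2.3 adds a condition: "All subjects who provide Informed Consent, are randomized and marked or implanted will be included in the intent-to-treat population". Protocol 2.2.5.1, in the paragraph that makes randomisation the entry point, ends: "Subjects who are screening failures or who are removed from the study prior to implantation will be excluded from analysis". SAP 10.3.1 defines the screen-failure count as one "which will include any patient who consented to participate whether they failed eligibility or withdrew prior to marking", and the SAP 12 list includes "Listing 16.2.1.2, Screen Failures and Reasons(s) for Failure, Randomized Subjects". Protocol 2.2.3 and 2.2.5.1 both exclude screening failures from analysis.

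**Non-implanted balloon men count as failures.** Protocol 2.2.3 says this of excluded men. Protocol 2.3.2 says it of balloon men who are not implanted, one or two of whom it anticipates. Protocol 2.3.4.2 says it for safety, of balloon men outside the per-protocol set. The SAP does not restate the rule. It specifies tipping-point analyses on ITT for safety (10.3.4.1.3) and efficacy (10.3.4.2.3), but Table 14.2.2.2, the safety tipping-point table, is labelled Per-Protocol, whereas Figure 14.2.5 is labelled ITT.

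**The concern.** The primary per-protocol set is asymmetric. Under SAP 9 it keeps every randomised control but only those balloon men who were marked and implanted as planned. The ITT sensitivity analyses exist to show whether that asymmetry matters, and they can do so only if ITT contains the men that the per-protocol set leaves out. Protocol 2.2.3 and 2.2.5.1, followed as written, remove some of them.

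There is time for such losses. Randomisation may precede implantation by up to 30 days (Protocol 2.2.8, SAP 7), and the surgeon and staff know the allocation (Protocol 2.2.5.1, SAP 5). Protocol 2.2.3 itself foresees a balloon man who is neither marked nor implanted because of a health concern. At stake is whether a programmer or site could, within the text, leave such a man out of the analysis meant to account for him.

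**Working it through.** **1. Apply each clause to the men concerned.**

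- *Balloon man lost between randomisation and marking.* In ITT under Protocol 2.3.2 and SAP 9. Out under Protocol 2.2.3. Under 2.2.5.1, in by the entry rule and out by the closing exclusion if he was removed. If he withdrew, SAP 10.3.1 counts him as a screen failure.
- *Balloon man excluded intraoperatively.* Protocol 2.2.6.5 puts implantation after marking, so he has normally been marked. He is in ITT under 2.3.2, SAP 9 and also 2.2.3, and SAP 10.3.1 does not reach him. Only the 2.2.5.1 exclusion could remove him.
- *Control man lost before marking.* In ITT, and in the per-protocol set, under SAP 9. Out of ITT under Protocol 2.2.3. SAP 9 describes the per-protocol set as a subset of ITT, and the 2.2.3 definition would break that nesting.

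The contradiction is therefore real, and sharpest for men lost before marking.

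**2. Reproduce the plan's figures.** Inputs from Protocol 2.3.4.4: 136 balloon and 68 control evaluable; efficacy 87.5% against a null of 75%; safety event rates 19% (balloon) and 21% (control); margin 15 points; one-sided alpha 0.025; 8% dropout.

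- Efficacy, exact binomial: P(X≥112 | 136, 0.75) = 0.0267 and P(X≥113 | 136, 0.75) = 0.0159, so success needs 113/136. Power P(X≥113 | 136, 0.875) = 0.949.
- Safety, Farrington-Manning: asymptotic power 0.851; exact enumeration 0.860.
- Joint: 0.949 × 0.851 = 0.808. Enrolment: 204/0.92 = 221.7, rounded up to 222.

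The stated 95%, 85%, 80% and 222 all reproduce to rounding.

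**3. Restore k non-implanted balloon men as failures.** Assume 136 implanted men and 68 controls are evaluable, and add k efficacy failures (or k safety events) to the balloon arm. Only k = 1 or 2 is anticipated in the protocol.

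Efficacy at the pass boundary, p = P(X≥113 | 136+k, 0.75):

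- k=0: 113/136, p=0.0159, pass
- k=1: 113/137, p=0.0240, pass
- k=2: 113/138, p=0.0351, fail

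One more success restores the pass at k=2: 114/138 gives p=0.0216. Under the design assumption P(X=113 | 136, 0.875) = 0.030. The chance of passing the failures analysis goes from 0.949 (k=0 and k=1) to 0.919 (k=2, where 114 are needed); the difference, 0.949 − 0.919 = 0.030, is that single outcome.

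Safety at its boundary, taking 14/68 control events as an illustration (21% of 68 is 14.3): 32/136 passes, 33/137 passes (p=0.023), 34/138 fails (p=0.029). By exact enumeration, the chance of passing goes from 0.860 to 0.836 (k=1) and 0.806 (k=2).

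**The case against.** The strongest reply is that the plan already has the right rule. Protocol 2.3.1 leaves the final analysis plan to the SAP, SAP 9 defines ITT as all randomised whether operated on or not, and Protocol 2.3.2 agrees. The conflicting wording is in the study-population and design sections of the protocol. SAP 10.3.1 is a disposition count, and no SAP sentence removes screen failures from ITT. The title of Listing 16.2.1.2 is weak evidence, since the same list has plain slips: Table 14.2.2.5 repeats its population label, and number 14.3.1.3.1 is used twice. All of this stands, and it limits the point to a conflict needing reconciliation.

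Two stronger readings are tempting. A reader might infer that the ITT tipping point is the only check on the per-protocol exclusions. The documents do not support that: Protocol 2.2.3, 2.3.2 and 2.3.4.2 separately promise an analysis with these men as failures. SAP 3.2 does not list its removal among the changes, and the efficacy tipping point, covering all possible imputations, includes the all-failures case. A reader might also infer that unblinded sites will relabel randomised men as screen failures so that they disappear. That requires joining an SAP disposition count to a protocol exclusion and overriding the SAP's ITT definition; the wording leaves room for it but does not direct it.

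Finally, the one or two anticipated men are all non-implanted balloon men. Those excluded intraoperatively mostly stay in ITT even under Protocol 2.2.3, so the figures in step 3 are an upper guide to what the pre-marking gap alone could do at that count.

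**Conclusion.** The contradiction is in the text and should be removed. Protocol 2.2.3 and 2.2.5.1 cannot both be followed alongside Protocol 2.3.2, SAP 9 and the failures rule, and SAP 10.3.1 with Listing 16.2.1.2 blurs the line between screen failures and randomised men. Omission of these men from the ITT check is a permitted reading, not the plan's settled rule.

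The size is small. At the anticipated count, one restored failure changes neither boundary result. Two reverse the efficacy sensitivity result only at exactly 113 successes, an outcome with probability about 0.03 under the design; the safety boundary example behaves in the same way. The primary tests, decided on the per-protocol set, and the sample size are unaffected. This rests on 136 and 68 evaluable men, on the protocol's forecast of one or two, and on restored men being counted as failures. The documents give no number for men lost between randomisation and marking; if it were larger, the effect would grow.

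**What to change.** - Define ITT as all randomised subjects throughout. In Protocol 2.2.3, delete the added condition of being marked or implanted; in 2.2.5.1, remove the exclusion as it applies to randomised men.
- In SAP 10.3.1 and Listing 16.2.1.2, limit screen failures to men who consented but were not randomised.
- Restate in the SAP the ITT analysis that counts non-implanted balloon men as failures, for both co-primary endpoints.
- Carry all randomised men in both tipping-point analyses (balloon arm only for efficacy), and relabel Table 14.2.2.2 as ITT to match SAP 10.3.4.1.3 and Figure 14.2.5.
- Report men randomised but not marked, and balloon men not implanted, by arm with reasons.

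The cost is wording, plus a full account of every randomised man. The sensitivity result may come out slightly less favourable.

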2.2.3.1 INCLUSION CRITERIA

Prospective subjects must meet *all* of the inclusion criteria to participate in this clinical study. To be included in the study, the subject must:

- Be at least 18 years of age;
- Have been histologically diagnosed with invasive adenocarcinoma of the prostate, at clinical stage T1-T3 that is locally confined or extracapsular with no posterior extension (i.e., not involving the rectum);
 - The stage of adenocarcinoma will be determined by biopsy. For patients who have very-low or low-risk prostate cancer (i.e., T1c or T2a, Gleason less than or equal to 3+3, and PSA less than 10 ng/mL), the biopsy may be taken up to 9 months prior to screening. For all others, the biopsy must be done no greater than 6 months prior to screening.
 - The presence/absence of posterior extension will be determined by MRI. For patients who have very-low or low-risk prostate cancer (T1c or T2a, Gleason less than or equal to 3+3, and PSA less than 10 ng/mL), the MRI may be taken up to 9 months prior to screening. For all others, the MRI must be taken no greater than 6 months prior to screening.
- Be scheduled for radiation therapy (XRT) for prostate cancer by means of IMRT and
- Be willing to adhere to the follow-up schedule and protocol requirements.

2.2.3.2 Exclusion Criteria

Prospective subjects must **not** meet *any* of the exclusion criteria to participate in this clinical study. These include:

- Pelvic lymph node radiotherapy is planned;
- Any prior invasive malignancy (except non-melanomatous skin cancer) unless the subject has been disease free for a minimum of 5 years;
- Prior radical prostatectomy;
- Prior cryosurgery or radiotherapy for prostate cancer, or other local therapy for prostate cancer;
- Prior radiotherapy to the pelvis, including brachytherapy;
- American Urological Assn. (AUA) Symptom Score ≥ 20 ;
- Active inflammatory bowel disease;
- Known or suspected rectal carcinoma;
- History of prior surgery involving the rectum or anus;
- Venereal warts in the region;
- Prior surgical procedure involving the peri-rectal and/or peri-prostatic area;
- Current urinary tract infection;

- Acute or chronic prostatitis;
- Acute infection requiring intravenous antibiotics at the time of screening;
- Uncontrolled bleeding disorders;
- Unsuitability for anesthesia in the opinion of the anesthesiologist;
- Currently taking anticoagulants or NSAIDS that cannot be stopped for sufficient time prior to the implantation procedure;
- EU citizens may not be enrolled by sites located at any site that is not GDPR compliant;
- Currently incarcerated or
- Participation in any other investigational drug, biologic or medical device study within the 30 days prior to the study surgery.

Intra-operative exclusion criteria for the balloon arm subjects only:

• Inability to perform proper dissection between prostate and rectum.

2.2.4 REQUIREMENTS FOR STUDY SITES

- Sites must use IMRT with marking inserted by transperineal approach;
- Sites must follow the contouring instructions, which will be provided separately. These instructions will be used at all participating sites for all enrolled subjects in both arms;
- Sites must perform weekly positioning verification during the XRT;
- Sites must use XRT protocols, where the prescription dose is biologically equivalent to 78-81 Gy in 1.8-2 Gy fractions;
- Sites must perform high resolution CT scans at ≤ 2 mm slice thickness **and**
- Sites must export copies of those CTs (axial and sagittal images) in DICOM format to allow for Core Lab analysis of appropriate visits.

2.2.5 STUDY DESIGN

2.2.5.1 OVERALL STUDY DESIGN

This study will be a prospective, multi-center, randomized, double-arm, single blind, concurrently controlled study to assess the safety and efficacy of the BioProtect Balloon Implant System in prostate cancer subjects undergoing radiotherapy by means of IMRT.

Subjects will be randomized in a 2:1 ratio (balloon implantation:control) to receive either IMRT +marking + balloon implantation or IMRT +marking. The balloon will be inserted during the same session of the marking.

Subjects will be blinded to study assignments. It is not practical to blind the surgeon or surgeon's staff since they will participate in the insertion procedure and/or be responsible for

maintaining source documentation. Additionally, the core lab cannot be blinded since the balloon will be visible on the CT images.

All subjects enrolled in the study will be included in an "intent-to-treat" analysis regardless of failure to complete the required follow-up examinations. Subjects will be considered enrolled in the study for the purposes of an intent-to-treat analysis only after they have provided Informed Consent and have been randomized. Preliminary data will be captured for subjects excluded intraoperatively, documenting the reason(s) for exclusion. It is anticipated that very few, if any, subjects will be excluded intraoperatively. Sites will maintain a log of screening failures, documenting the reason for failure. Additionally, subjects who are randomized but not implanted (e.g., due to an adverse event that prevents or significantly delays their radiation treatment) may be removed from the study. Such removals will be documented and reported appropriately. Subjects who are screening failures or who are removed from the study prior to implantation will be excluded from analysis.

This study will utilize a core laboratory for analysis of CT images. Post implantation CT images for the *Balloon Group* will be compared to pre-implantation images to demonstrate the change in distance and potential for rectal protection provided by the balloon.

